9.2 Study Population

9.2.1 Inclusion Criteria

The patient must meet all of the following inclusion criteria to be eligible for enrolment into the study:

Demographics

1. Female or male ≥ 4 years of age.
2. Body weight ≥ 10 kg, and within the expected range for an RTT patient, based on age and height.

Diagnostic

3. Diagnosis of Rett syndrome based on consensus clinical criteria (Neul et al, 2010; Appendix 4). A test for MECP2 mutations (Xq28) will be performed if results from an accredited laboratory are not available; selection for the trial is not contingent on the results of the MECP2 test. Patients with known MECP2 duplications will not be eligible.
4. One or more of the following breathing dysfunctions: periodic apnea during wakefulness; intermittent hyperventilation; breath holding spells; air swallowing; forced expulsion of air or saliva.
5. Patient meets all of the following criteria related to breathing abnormalities:
 - a. Parent report of 10 episodes or more of breathing abnormality per day during wakefulness in the week prior to the screening visit;
 - b. Time per hour spent on normal breathing is less than 90% of the total time per hour of wakefulness (i.e., $\geq 10\%$ of the time should be abnormal breathing);

- c. Has at least 10 episodes of breathing dysrhythmia, defined by episodes ≥ 10 seconds of breath holding (apnea), per hour, during cardiorespiratory monitoring (performed with home/ambulatory monitoring system during screening period).
6. Stable medication regimen for 4 weeks prior to beginning the study (if receiving services - physical, occupational, or speech therapy - subjects must be on a stable regimen of these services for 3 months prior to beginning the study). Female patients of childbearing potential are to use adequate contraception as recommended by their Health Care Provider (see [Section 13.1.8](#)).

Procedural

7. Parent/legal guardian/representative has provided written consent prior to the patient participating in the study. Where feasible, consent or assent for patients less than 18 years of age, has also been provided by the patient.
8. Ability to take study medication provided either as capsules or combined with food/drink.
9. Patient is cooperative, willing to complete all aspects of the study, and capable of doing so with assistance of a caregiver.
10. Caregiver is able to understand the instructions and fully participate.

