Variable	Clinically Notable Values
Protein	Increase of 2 units
Glucose	Increase of 2 units

CLINICALLY NOTABLE VITAL SIGNS VALUES

Parameter	Unit	Decrease	Increase
Sitting/Supine SBP	mmHg	Value ≤ 90 and ≥ 20 decrease from Baseline.	Value ≥ 180 and ≥ 20 increase from Baseline
Sitting/Supine DBP	mmHg	Value ≤ 50 and ≥ 15 decrease from Baseline.	Value ≥ 105 and ≥ 15 increase from Baseline
Orthostatic Hypotension (based on standing SBP/DBP)	mmHg	Decrease in SBP/DBP from Supine to Standing position exceeding > 30mmHg	NA
Sitting pulse rate	bpm	Value ≤ 50 and ≥ 15 decrease from Baseline	Value ≥ 120 and ≥ 15 increase from Baseline
Weight	kg	≥ 7% decrease from Baseline.	≥ 7% increase from Baseline.
Respiration rates*	Breaths/minute	< 12	> 25
Temperature	°C	NA	Value ≥ 38.3 and ≥ 1.1 increase from Baseline.
Temperature	°F	NA	Value ≥ 101.0 and ≥ 2.0 increase from baseline

* For respiration rate values are relevant, not decrease/increase.

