Recently, a study was performed in 12 female patients with Rett syndrome, ages 3-10, to evaluate the safety, pharmacokinetics and efficacy of mecasermin ([Khwaja et al, 2014](#)). Eight of the 12 patients were diagnosed with breathing abnormalities (e.g. air expulsion, breath holding, hyperventilation, apnea) at baseline. Automated measurements of cardiorespiratory parameters were performed using RIP and ECG, and recorded using the BioRadio. Data collected with this system was used to calculate various respiratory parameters, including total respiratory cycle times (Ttot) and inspiratory peaks (amplitude >20% above the typical amplitude). Ttot was categorized as normal, apneic or tachypneic based on aged-defined norms. Clinically significant apnea was defined as a pause in inspiration ≥ 10 seconds, and the number of these events per hour (apnea index) was calculated for each patient at baseline (mean \pm SE: 10.11 \pm 19.34) and at subsequent visits. In addition, hyperventilation was defined as ≥ 5 consecutive tachypneic breaths, with amplitude greater than the typical amplitude, and the number of these events per hour (hyperventilation index) was calculated for each patients at baseline (mean \pm SE: 3.55 \pm 6.71) and at subsequent visits. These measurements, which were made using the BioRadio and RIP, showed good agreement with clinicians' assessments using plethysmography.

Regulatory status of the BioRadio

The BioRadio complies with FCC Part 15 rules and conforms to FDA guidelines for use as a research tool in capturing electronic data in clinical trials. The Quality Management System for the device complies with the requirements of ISO13485:2003, and it is CE marked in Europe for research purposes. The BioRadio is not a medical device, but it complies with the Radio and Telecommunications Terminal Equipment (R&TTE) Directive 1999/5/EC and the Electromagnetic Compatibility (EMC) Directive 2004/108/EC, which are part of the product electrical safety requirements stated within IEC 60601-1.

The BioRadio is available for sale in the US, Europe and Canada. The development of the device has been funded in part by the NIH and 25 collaborating institutions have been involved in its testing. Results of studies using the BioRadio have been presented in over 65 peer-reviewed publications and presentations.

Summary

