17.5. VITAL SIGNS

The following vital signs measurements will be reported for this study:

- Systolic Blood Pressure (mmHg)
- Diastolic Blood Pressure (mmHg)
- Pulse (bpm)
- Respiratory Rate (breaths/min)
- Body Temperature (⁰C)

The following summaries will be provided for vital signs data:

- Actual values and change from baseline by visits and timepoints
- Incidence of clinically notable vital signs values at Day 1, Day 15, Week 24 and End of Study visits as defined in Appendix 3 of the SAP
- Listing of patients' vital signs

The descriptive statistics for actual measurement and change from baseline will be presented by treatment group and timepoints at scheduled visits.

Document:	\\ieedc-vnasc01\BIOSdata\Newron\Sarizotan\PXA76395\Biostatistics\Documentation\SAP		
Author:	[name]	Version Number:	V2
		Version Date:	[30March2020]
Template No:	CS_TP_BS016 – Revision 4	Reference:	CS_WI_BS005
Effective Date:	01Apr2016		

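### Respiration rate is the one vital sign called notable on its value alone, so in patients enrolled for abnormal breathing the planned incidence table can dilute a new-onset difference between arms

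*Protocol*

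**What the plan says.** The vital-signs table in Protocol Appendix 2 has eight rows, with temperature entered twice. Systolic pressure needs a limit and a change ("Value ≤ 90 and ≥ 20 decrease from Baseline"). Diastolic pressure and pulse have the same form ("Value ≤ 50 and ≥ 15 decrease from Baseline"), and so does temperature ("Value ≥ 38.3 and ≥ 1.1 increase from Baseline"). Weight is a change from baseline only ("≥ 7% decrease from Baseline"), and orthostatic hypotension is a supine-to-standing change. Respiration rate is below 12 or above 25 breaths/min with no change condition, and the footnote states this directly: "For respiration rate values are relevant, not decrease/increase".

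SAP Appendix 3 carries the same limits and the asterisk, but not the footnote text. SAP 17.5 plans "Incidence of clinically notable vital signs values at Day 1, Day 15, Week 24 and End of Study visits", using that appendix. It also plans actual values and change from baseline by visit and timepoint, and a patient listing. It plans no shift table for vital signs, whereas SAP 17.3 plans one for laboratory data.

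Protocol 9.2.1 requires "One or more of the following breathing dysfunctions: periodic apnea during wakefulness; intermittent hyperventilation; breath holding spells" or another listed dysfunction. It also requires at least 10% of waking time in abnormal breathing and at least 10 apneas of 10 seconds or more per hour.

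**The concern.** A table headed incidence will be read as events arising on treatment. Under this rule, a patient at 28 breaths/min before the first dose and at 28 at Week 24 counts as notable at Week 24. A patient already outside a limit cannot become newly notable on that side, even if the rate moves further out. For pressure, pulse, temperature and weight, the change condition guards against this.

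Respiration rate is the vital sign closest to the disease and to the drug's target. Protocol 7.1.1 describes alternating hyperventilation and apnea in Rett syndrome, so either limit could be crossed because of the disease. It also reports that sarizotan raised breathing frequency in mutant mice, so the variable may move on treatment. Protocol 15.2.5 compares sarizotan with placebo on the proportion of patients with clinically significant abnormalities in safety parameters, so a diluted count could carry into a planned comparison. At stake is whether a real difference in new onset would be visible in the table meant to show it.

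**Working it through.** The plan gives no figure here to reproduce. No sample size, power or error rate depends on this rule.

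**Step 1: classify the rows of Protocol Appendix 2.**
- Limit plus change from baseline: systolic pressure, diastolic pressure, pulse, temperature in °C, temperature in °F (5 rows).
- Change from baseline only: weight (1 row).
- Postural change: orthostatic hypotension (1 row).
- Value only: respiration rate (1 row).

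The total is 5 + 1 + 1 + 1 = 8. Respiration rate is the only value-only row, and SAP Appendix 3 gives the same classification.

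**Step 2: size of the dilution.** Let b be the share outside 12–25 at baseline who stay outside. Let e be new onset on placebo among the rest, and e + d new onset on drug.
- Placebo as tabulated: b + (1 − b)e.
- Drug as tabulated: b + (1 − b)(e + d).
- Difference: (1 − b)d.

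The result does not depend on e. With d = 20 points, the difference is 0.8 × 20 = 16 at b = 20%, 0.6 × 20 = 12 at b = 40%, and 0.4 × 20 = 8 at b = 60%.

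**Step 3: what that looks like with 43 per arm** (Protocol 9.1). Assume e = 5% and d = 20 points. Power uses the normal approximation for two proportions at two-sided 0.05: Φ[(difference − 1.96 × SE₀)/SE₁], with SE₀ pooled and SE₁ unpooled. At b = 20%, the rates are 0.24 and 0.40, SE₀ = √(0.32 × 0.68 × 2/43) = 0.1006 and SE₁ = √[(0.24 × 0.76 + 0.40 × 0.60)/43] = 0.0991. Power is Φ[(0.16 − 0.1972)/0.0991] = 0.35.

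| b (assumed) | Placebo v drug, as planned | Risk ratio | Nominal power |
|---|---|---|---|
| 0 | 5% v 25% | 5.0 | 0.75 |
| 20% | 24% v 40% | 1.67 | 0.35 |
| 40% | 43% v 55% | 1.28 | 0.20 |
| 60% | 62% v 70% | 1.13 | 0.12 |

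The power column shows only how visible the contrast would be. The SAP plans no test on this table.

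**Step 4: what a newly-outside count would show.** Among patients inside the limits at baseline, the rates return to 5% v 25%, but on 43 × (1 − b) patients per arm: 34.4, 25.8 and 17.2 for b = 20%, 40% and 60%. The same formula on those numbers gives 0.65, 0.52 and 0.37. The full 20-point difference is recovered, though not all of the lost precision.

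**The case against.** The case on the other side is substantial.

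- **The value-only basis is deliberate.** Protocol Appendix 2 attributes the list to FDA division guidelines, and the footnote is explicit. That explains the rule. It does not show that an incidence table ignoring baseline suits patients selected for abnormal breathing.
- **The baseline share is unknown.** A reader might infer that existing disease will fill the table. The documents do not support that: entry rests on parent report, time in abnormal breathing and monitored apneas, not on resting rate, and no baseline rates are given. Every b above is an assumption.
- **Cancellation.** A reader might infer that fewer high rates on drug could offset new low rates in one count. Both tables put the limits in separate Decrease and Increase columns, and nothing says they will be combined. Cancellation arises only if they are.
- **Momentary readings.** A reader might infer that frequent apneas routinely push a spot count below 12. Overlap with an apnea is not the same as crossing the limit. In an assumed one-minute count, losing a full 10 seconds takes 20/min to 20 × 50/60 = 16.7, and one such apnea crosses 12 only if the underlying rate is below 12 × 60/50 = 14.4. If excursions are momentary, though, baseline status separates disease from drug less cleanly, and a newly-outside count helps less. This limit on the remedy stands.
- **Age.** A reader might infer that one range from age 4 contradicts Protocol Appendix 5, where "Ttot was categorized as normal, apneic or tachypneic based on aged-defined norms". That sentence describes breath timing in a cited earlier study. The documents supply no age bands, and blood pressure and pulse limits are also fixed.
- **Other outputs exist.** These are mean change, listings, adverse events (which include worsening of existing abnormalities), unblinded safety board review, and BioRadio measures of apnea, hyperventilation and desaturation. They mitigate the problem, and the BioRadio data measure breathing far better than a spot rate. None gives new-onset incidence of notable respiration rate by arm.

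**Conclusion.** The concern holds, within limits. Respiration rate is the only vital-sign row judged on value alone, and it has neither a change condition nor a shift table. Followed as written, SAP 17.5 counts values already present before dosing as on-treatment incidence. If a share b stays outside the limits, a new-onset difference shrinks by (1 − b): 20 points becomes 16, 12 or 8 for b of 20%, 40% or 60%. These figures assume that affected patients remain outside the limits at the visit and that the drug effect appears only in the others.

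This is dilution of a descriptive safety contrast. Randomisation spreads baseline disease across arms, so no arm is favoured, and neither the primary analysis nor the win criterion is touched. The change is worth making because it is cheap, not because the documents show that a signal would be lost.

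**What to change.** In SAP 17.5 and Appendix 3, before unblinding:

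1. Keep the present limits and the present count. Replacing it with newly outside patients only would miss further worsening, such as a patient at 11 who falls to 5 or one at 26 who rises to 45.
2. For respiration rate, add the number newly outside each limit by arm, with below 12 and above 25 shown separately and patients inside that limit at baseline as denominator.
3. Add a baseline-to-visit shift table (below 12, 12 to 25, above 25) by arm, with baseline prevalence.
4. State which baseline reading is used. Protocol 11.4.2 asks for repeated readings, Protocol 12.1.2 describes averaging for blood pressure and pulse only, and SAP 6.2 defaults to the last value before dosing.
5. Restore the protocol footnote in SAP Appendix 3, where the asterisk now points to nothing.

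All data are already collected. The cost is one extra table, a little programming, and small counts per cell with about 43 patients per arm.

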19.4 APPENDIX 4: RTT Diagnostic Criteria

Revised Diagnostic Criteria for Rett Syndrome (Neul et al, 2010)

RTT Diagnostic Criteria 2010	
Consider diagnosis when postnatal deceleration of head growth observed.	
Required for typical or classic RTT	
1	A period of regression followed by recovery or stabilization *
2	All main criteria and all exclusion criteria
3	Supportive criteria are not required, although often present in typical RTT
Required for atypical or variant RTT	
1	A period of regression followed by recovery or stabilization *
2	At least 2 out of the 4 main criteria
3	5 out of 11 supportive criteria
Main Criteria	
1	Partial or complete loss of acquired purposeful hand skills.
2	Partial or complete loss of acquired spoken language **
3	Gait abnormalities: Impaired (dyspraxic) or absence of ability.
4	Stereotypic hand movements such as hand wringing/squeezing, clapping/tapping, mouthing and washing/rubbing automatisms
Exclusion Criteria for typical RTT	
1	Brain injury secondary to trauma (peri- or postnatally), neurometabolic disease, or severe infection that causes neurological problems ***
2	Grossly abnormal psychomotor development in first 6 months of life #
Supportive Criteria for atypical RTT ##	
1	Breathing disturbances when awake
2	Bruxism when awake
3	Impaired sleep pattern
4	Abnormal muscle tone
5	Peripheral vasomotor disturbances
6	Scoliosis/kyphosis
7	Growth retardation
8	Small cold hands and feet
9	Inappropriate laughing/screaming spells
10	Diminished response to pain
11	Intense eye communication - "eye pointing"

* Because *MECP2* mutations are now identified in some individuals prior to any clear evidence of regression, the diagnosis of "possible" RTT should be given to those individuals under 3 years old who have not lost any skills but otherwise have clinical features suggestive of RTT. These individuals should be reassessed every 6–12 months for evidence of regression. If regression manifests, the diagnosis should then be changed to definite RTT. However, if the child does not show any evidence of regression by 5 years, the diagnosis of RTT should be questioned.

** Loss of acquired language is based on best acquired spoken language skill, not strictly on the acquisition of distinct words or higher language skills. Thus, an individual who had learned to babble but then loses this ability is considered to have a loss of acquired language.

Amend. 1, 19Jan2016; Amend. 2, 18May2016; Amend. 3, 21Oct2016; Amend. 4, 03Mar2017; Amend. 5, 29Mar2017; Amend. 6, 13Apr2017; Amend. 7, 02Oct2017; Amend. 8, 02Nov2017; Amend. 9, 11Feb2018; Amend. 10, 29Nov2018; Amend. 13, 10Dec2019; Amendment 14, 17 March 2020, Clean, Final

Revised Diagnostic Criteria for Rett Syndrome (continued)

There should be clear evidence (neurological or ophthalmological examination and MRI/CT) that the presumed insult directly resulted in neurological dysfunction.

#

Grossly abnormal to the point that normal milestones (acquiring head control, swallowing, developing social smile) are not met. Mild generalized hypotonia or other previously reported subtle developmental alterations¹⁶ during the first six months of life is common in RTT and do not constitute an exclusionary criterion.

##

If an individual has or ever had a clinical feature listed it is counted as a supportive criterion. Many of these features have an age dependency, manifesting and becoming more predominant at certain ages. Therefore, the diagnosis of atypical RTT may be easier for older individuals than for younger. In the case of a younger individual (under 5 years old) who has a period of regression and ≥ 2 main criteria but does not fulfill the requirement of 5/11 supportive criteria, the diagnosis of "probably atypical RTT" may be given. Individuals who fall into this category should be reassessed as they age and the diagnosis revised accordingly.

19.5 APPENDIX 5: Cardiorespiratory Measurements using the BioRadio

Validation of the BioRadio System for Use in Remote Monitoring of Respiratory Function

The BioRadio™ system will be used in the first sarizotan study in Rett syndrome patients (Study Sarizotan/001/II/2015) to assess respiratory function, including changes in the frequency of apnea episodes, which will be the primary efficacy parameter.

What is the BioRadio?

[figure not shown]
The BioRadio is a wireless data acquisition system developed by Great Lakes NeuroTechnologies (Cleveland, OH) that is capable of recording, displaying and analyzing physiological signals in real time, e.g. measuring electrocardiogram (ECG), respiratory, electro-encephalogram (EEG), electromyogram (EMG) and pulse oximetry parameters. Physiological signals are amplified, sampled and digitized, and can be wirelessly transmitted to a computer via Bluetooth receiver and/or recorded to onboard memory for post-analysis.

What does it consist of?

The BioRadio consists of a Primary Module, which has 4 (differential) or 8 (single-ended) channels, allowing measurement of multiple parameters simultaneously, and an optional Sensor Pod which has an input for a pulse oximeter and another sensor. A differential channel on the Primary Module can be configured for respiratory inductance plethysmography (RIP) using inductive bands. This configuration will be used in the sarizotan study; an additional channel will be used for pulse oximetry. The BioRadio is worn by the patient and uses wireless technology to transfer data from sensors attached to the body, allowing the patient to move about freely during the recording process.

How does it work?

The BioRadio system employs RIP technology to measure respiratory functional parameters, including apnea index, hyperventilation index, epoch apnea, respiratory rate, respiratory cycle time, and respiratory irregularity. Dual-band RIP is a technique that uses two elastic bands containing inductive coils, which wrap around the chest and abdomen of the patient, to calculate chest and abdominal expansion, respiratory rate, respiratory pattern and tidal volume. An alternating current is passed through the belt, generating a magnetic field. The act of breathing changes the cross-sectional area of the patient's body,

which in turn changes the shape of the magnetic field generated by the belt, inducing an opposing current that can be measured. The signal produced is linear and related to the change in cross-sectional area. The utility of dual-band RIP in measuring respiratory function is based on the premise that volume changes at the orofacial orifices are equal to the sum of the volume changes of the rib cage and abdominal compartments (Konno and Mead, 1967), thus measurements done using RIP are equivalent to those made using spirometry, when the RIP system is properly calibrated (Sackner et al, 1989).

How does it measure respiration?

Impedance pneumography, using low amplitude, high frequency, alternating currents between two recording electrodes has been extensively used to record thoracic movements during respiration. However impedance pneumography use is constrained by findings that indicate the electrical resistance of the rib cage tissues is less than air, and therefore the AC passing through the thoracic cavity reflects tissue impedance and provides an erroneous value for thoracic volume. Impedance pneumography is affected by

Amend. 1, 19Jan2016; Amend. 2, 18May2016; Amend. 3, 21Oct2016; Amend. 4, 03Mar2017; Amend. 5, 29Mar2017; Amend. 6, 13Apr2017; Amend. 7, 02Oct2017; Amend. 8, 02Nov2017; Amend. 9, 11Feb2018; Amend. 10, 29Nov2018; Amend. 13, 10Dec2019; Amendment 14, 17 March 2020, Clean, Final

motion and cardiogenic artifacts, and as the rib cage (RC) signal is dependent on posture, tidal volumes are difficult to estimate and the polarity of signals changes suddenly. This has led to increasing use of inductive plethysmography.

Respiratory inductive plethysmography has been used extensively as a non-invasive method for measuring respiratory volumes, particularly in the diagnosis of sleep-related breathing disorders (Cantineau et al, 1992; Bloch et al, 1997) and upper airway resistance syndrome (Loube et al, 1999). RIP has a number of advantages over impedance pneumography, which employs alternating current between two surface electrodes to record thoracic movements or volume changes at the rib cage (Landon, 2003). These advantages of RIP include greater accuracy and sensitivity, the ability to assess thoraco-abdominal coordination, and the minimization of motion artifact.

Validation studies of the BioRadio

The older RIP model was validated in patients and healthy volunteers for measurement of tidal volumes and respiratory lung volume by comparing it with data obtained with a pneumotachometer and spirometer as references (Valta et al 1992). A series of validation studies were performed for newer models (Respirace Plus™) of the RIP, where it was first calibrated using qualitative diagnostic calibration by comparison of signals obtained by the pneumotachometer and from the sum of the rib and abdominal cages (RC and AC). The newer model has also been validated by comparing its performance to the older RIP.

The Respirace Plus™ was evaluated both under clinical and laboratory conditions and compared with an earlier validated version (RespiGraph™) in the measurement of tidal volume, long-term end-expiratory lung volume (EELV) and changes in EELV induced by positive end-expiratory pressure (PEEP) in a study done by Leino et al (2001). In this study no significant differences were noted between RIP and the pneumotachometer with regard to measurements of tidal volume in spontaneously breathing volunteers and mechanically ventilated patients with acute lung injury, or in measurements of PEEP-induced changes in EELV in acute lung injury patients.

A portable RIP has been tested in monitoring of ventilation during exercise in unrestrained subjects, including 20 healthy volunteers, 6 patients with COPD, and 5 patients with congestive heart failure (Clarenbach et al, 2005). An elastic body garment (LifeShirt™; VivoMetrics) containing the inductance sensors encircling the rib cage and abdomen was used and connected to a portable, battery-powered device which was connected to sensors measuring pulse oximetry, ECG and body movements, in addition to RIP. A comparison between measurements obtained with the portable RIP and a flowmeter (pneumotachograph) over the course of progressive exercise to exhaustion (treadmill) showed good agreement for respiratory cycle time, tidal volume, and minute ventilation for both healthy volunteers and patients with breathing difficulties. The RIP monitor was able to identify differences in breathing patterns between healthy volunteers and patients with pulmonary or cardiac disease.

The new RIP was also validated during controlled ventilation post operatively in patients with chronic obstructive pulmonary disease (COPD) and in acute lung injury, by comparing results with those obtained from a pneumotachometer (Neumann et al, 1998).

Use of the BioRadio to measure respiratory indices in patients

The guidelines for the use of unattended portable monitors in the diagnosis of obstructive sleep apnea published by the Portable Monitoring Task Force of the American Academy of Sleep Medicine, recommend the use of RIP, as opposed to other non-invasive techniques, e.g. piezo sensors, strain gauges and thoracic impedance, for measuring respiratory effort, in particular for scoring hypopnea, in the laboratory setting (Collop et al, 2007).

A study in newborn infants found that thoracic impedance monitors were less sensitive than RIP in monitoring respiratory events related to obstructive sleep apnea (Brouillette et al, 1987). Similarly, a study

Amend. 1, 19Jan2016; Amend. 2, 18May2016; Amend. 3, 21Oct2016; Amend. 4, 03Mar2017; Amend. 5, 29Mar2017; Amend. 6, 13Apr2017; Amend. 7, 02Oct2017; Amend. 8, 02Nov2017; Amend. 9, 11Feb2018; Amend. 10, 29Nov2018; Amend. 13, 10Dec2019; Amendment 14, 17 March 2020, Clean, Final

performed comparing RIP and other methods, e.g. strain gauges and impedance pneumography, to a pneumotachograph in measuring breath amplitude and tidal volume in newborn infants demonstrated that RIP showed more accurate and consistent measurements in both the supine and prone positions, compared with the other methods ([Adams et al, 1993](#)).

A non-calibrated RIP has been used in a study in monkeys to measure phase angle (relationship of thoracic to abdominal movements during breathing) to assess the effects of inspiratory load on thoraco-abdominal asynchrony, as is observed in infants and small children with acute upper airway obstruction ([Hammer et al, 1995](#)). A good correlation was observed between the phase angle measurements, calculated based on data from the RIP, and inspiratory load, i.e., phase angle increased continuously with higher inspiratory loads.

Use of the BioRadio in patients with Rett Syndrome

Recently, a study was performed in 12 female patients with Rett syndrome, ages 3-10, to evaluate the safety, pharmacokinetics and efficacy of mecasermin ([Khwaja et al, 2014](#)). Eight of the 12 patients were diagnosed with breathing abnormalities (e.g. air expulsion, breath holding, hyperventilation, apnea) at baseline. Automated measurements of cardiorespiratory parameters were performed using RIP and ECG, and recorded using the BioRadio. Data collected with this system was used to calculate various respiratory parameters, including total respiratory cycle times (Ttot) and inspiratory peaks (amplitude >20% above the typical amplitude). Ttot was categorized as normal, apneic or tachypneic based on aged-defined norms. Clinically significant apnea was defined as a pause in inspiration ≥ 10 seconds, and the number of these events per hour (apnea index) was calculated for each patient at baseline (mean \pm SE: 10.11 \pm 19.34) and at subsequent visits. In addition, hyperventilation was defined as ≥ 5 consecutive tachypneic breaths, with amplitude greater than the typical amplitude, and the number of these events per hour (hyperventilation index) was calculated for each patients at baseline (mean \pm SE: 3.55 \pm 6.71) and at subsequent visits. These measurements, which were made using the BioRadio and RIP, showed good agreement with clinicians' assessments using plethysmography.

Regulatory status of the BioRadio

The BioRadio complies with FCC Part 15 rules and conforms to FDA guidelines for use as a research tool in capturing electronic data in clinical trials. The Quality Management System for the device complies with the requirements of ISO13485:2003, and it is CE marked in Europe for research purposes. The BioRadio is not a medical device, but it complies with the Radio and Telecommunications Terminal Equipment (R&TTE) Directive 1999/5/EC and the Electromagnetic Compatibility (EMC) Directive 2004/108/EC, which are part of the product electrical safety requirements stated within IEC 60601-1.

The BioRadio is available for sale in the US, Europe and Canada. The development of the device has been funded in part by the NIH and 25 collaborating institutions have been involved in its testing. Results of studies using the BioRadio have been presented in over 65 peer-reviewed publications and presentations.

Summary

Respiratory inductive plethysmography has been used extensively over the past 25 years as a reliable method for non-invasive measurement of respiratory functional parameters. Good agreement has been demonstrated in a large number of studies between measurements taken using RIP and direct measurements using spirometry or pneumotachography. Coupling of RIP with a portable wireless data acquisition system such as the BioRadio allows respiratory measurements to be made in freely moving subjects. The utility of this combination has been demonstrated in a recent study in Rett syndrome patients, where cardiorespiratory monitoring was performed using the BioRadio and RIP, including measurement of apnea and hyperventilation indexes ([Khwaja et al, 2014](#)).

